3.2.1 Screening. Candidates will undergo a screening to assess co-morbidities and to identify inclusion and exclusion criteria. Standard questionnaires and screening instruments include the Research

Diagnostic Criteria for TMD (TMD-RDC) (Dworkin and LeResche, 1992), Jaw Function Limitation Scale (JFLS) (Ohrbach et al., 2008), the TMD Pain Screener (Gonzalez et al., 2011), Measure of Symptoms Sleep Scale (MOS), Perceived Stress Scale (PSS). Additionally, a brief clinical exam will be performed to evaluate dental and medical health, including an intra-oral and extra-oral head and neck examination, heart rate and blood pressure. Subjects meeting the acceptance criteria will be randomly assigned to one of the two groups (**Table 1**) using stratified randomization procedures (Suresh, 2011). Subjects will then have alginate impressions taken, and impressions will be poured up in stone. The models will be used either to fabricate the MI BS or to assess SOVA appliances for fabrication efficacy.

3.2.3. Splint delivery. For the SOVA group, subjects will be asked to fabricate SOVA devices in the clinical laboratory while receiving feedback from trained and calibrated study ‘instructors’. Fabrication will proceed according to manufacturer instructions. Calibrated instructors will be blinded to the study’s objectives, as will subjects. A “Michigan” acrylic bite splint will be fabricated using standard clinical practice and checked for fit and quality on subjects assigned to the MI BS group.

3.2.4 Subjective fabrication assessment. Standardized questionnaires will be provided to participants and will cover issues of ease of fabrication, ease of instructions, and other related issues for the devices. Box scales will be used to evaluate items individually and separately.

3.2.5 Quantitative fabrication assessments. Four aspects of fabrication will be evaluated by investigators: (1) stability—does the device move independently of the maxilla and is the mandible stabilized by the device, (2) retention—does the device resist displacement, (3) tissue adaptation—how much spacing exists between the maxilla and the device and between the device and mandible, and (4) health of the teeth, gingival, tongue, palate and lips.

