3.2.5a. Stability and retention will be quantitatively assessed with jaw movement (custom jaw tracking devices in conjunction with a MaxTraq motion analysis system [Innovision, Columbiaville, MI] and EMG [LabChart, ADInstruments, Colorado Springs, CO] data) and force sensors (T-scan, Tektronix, South Boston, MA). For position-stability assessment, maxilla, mandible and the splint will be simultaneously recorded from at least three sites each (to capture 6 degrees of movement freedom). Subjects will clench, grind, perform closed border movements and vacuous chewing (verified with EMG and force sensors). For retention assessment, subjects will perform a series of tests designed to dislodge the device, e.g., tapping, forced blowing, coughing, chewing on gum. Stability and retention indices will be created based on whether device movements vary independently of jaw movements and applied bite forces, and how force sensor output varies during dislodgement exercises. (Note, the force sensors will be placed between the device and the maxilla, so that reductions in sensor output will indicate that the device is being dislodged.) Deviations will be used to form standardized indices of stability and retention, with smaller values representing greater stability and retention.

3.2.5b. Tissue adaptation will be assessed by using a 3D laser scanner. The occlusal, facial and lingual surfaces of the upper arch will be scanned as will the inner surface of the night guards. An index of

[figure not shown]

Fig. 2. Overview of planned studies (see text).

adaptation will be developed based on the volumetric spaces separating the teeth from the device, using topological software. Smaller volumes will represent better tissue adaptation. Volumetric indices will be compared between devices via ANOVA or appropriate statistical methods.

3.2.5c Tissue health will be assessed via appropriate, standard methods currently used in cariology and periodontology clinical studies (Monse et al., 2012; Tirapellia et al., 2010). Baseline measurements will be compared with post-device wear measurements. Between-group differences will be studied with a repeated measures ANOVA or appropriate statistical methods.

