3.2.6 Compliance assessment. Compliance assessments will focus on: (1) how often the device is worn, (2) whether the device is removed at inappropriate times during the night, (3) whether alternative devices are used. Compliance will be assessed via subject self-report (daily log), nocturnal EMG recording devices and microwear methods. Subjects would be blinded to the purpose of the technological methods. Occlusal microwear patterns are unique to the surfaces against which occlusion occurs, and the microwear changes on a daily basis (Ungar et al., 2003). Hence, microwear assessment provides definitive evidence regarding splint compliance.

3.2.7 Functional efficacy. Two questions will be addressed under functional efficacy: (1) does the device alter bruxing activity, and (2) how do the teeth and device hold up under bruxing activity. Some of the technology used for compliance assessment, above, can be used here. 'Gold standard' methods for evaluating bruxing activity rely on polysomnography (PSG) and EMG activity; therefore, it will be important to employ these technologies for purpose of peer-review publications. To address the second question, how do the teeth hold up, 3-D laser scanning technology will be used to measure changes in macroscopic tooth structure, and confocal microscopy and scale-sensitive fractal analysis will be useful for addressing microwear.

3.2.8 User satisfaction. This will be assessed through a series of standardized questionnaires adopted from other clinical studies, e.g., the Oral Health Impact Profile (Slade and Spencer, 1994), the Tampa Scale for Kinesiophobia: TMD (Visscher et al., 2010), the TMD pain screener (Gonzalez et al., 2011). Questionnaires used in the SISU field tests (SISU mouthguards preliminary results), as well as forced choice, box scales and statistical methods developed in another study (Lin, 2008; Lin et al., 2013) will also prove useful for assessment of patient satisfaction. Also such questions as, does the device hurt or pinch anywhere, does your bite feel 'off' when you first remove the guard, how often do you take out the splint before the night is over, do you experience excessive salivation or dry mouth, do you ever wake up with the splint out for unknown reasons, does the device build up plaque and other deposits through time, do you ever just feel like not wearing it and if so why not, will be used to assess specific aspects of user satisfaction.

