5. BUDGET

Personnel

No personnel costs are being requested. The project will be carried out by dental students in the Pathways program of the school of dentistry and undergraduate pre-dental students who will be earning course credit. In this way, these costs can be curtailed.

Equipment

Funds are being requested for a sleep monitoring system (*Biocapture*, EMG sleep system) in order to evaluate compliance and efficacy issue (**Table 2**). The system monitors polysomnographic (PSG) variables to confirm sleep and bruxing events and is a clinical research standard and necessity. The system is critical for evaluating the night guard for compliance and functional efficacy in the home environment. No such system current exists in the [name] laboratory.

Amplifiers and jaw tracking system upgrades are being requested for evaluation of bite splint stability and retention in the controlled laboratory setting (Table 2). The EMG system to which the amplifiers will be attached, will be purchased through other funding mechanisms in order to reduce costs to Delta Dental. Funds for the jaw tracking system represent an upgrade to an existing system; the upgrade will automate the analysis. The automation is critical, because it will allow students to do the data acquisition; otherwise non-automated analysis requires trained experts, which would require substantial personnel costs.

Funds are being requested for a *T-scan* bite-force analysis system. This system, currently unavailable in the [name] laboratory, is the only system in existence that can reliably and quantitatively check how intra-oral forces impact stability and retention of the splint. Without this system, these aspects of the project would be difficult if not impossible to do.

All equipment and upgrade prices reflect 20% academic price reductions.

Supplies

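### No masking of outcome assessors, readers or analysts to device is described, including for the outcomes that need judgement, although much of the material is stored and could be scored under a code

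*Combined protocol and SAP*

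**What the plan says.** Section 3.2.5 covers stability, retention, tissue adaptation and tissue health, and states: "Four aspects of fabrication will be evaluated by investigators". It says nothing about whether those investigators know the device.

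Blinding is mentioned twice:

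- Section 3.2.3, on fabrication of the SOVA device: "Calibrated instructors will be blinded to the study’s objectives, as will subjects".
- Section 3.2.6, on compliance: "Subjects would be blinded to the purpose of the technological methods".

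Neither sentence concerns people who score or analyse outcomes, and neither concerns knowledge of arm.

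On how outcomes are captured:

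- Section 3.2.5a: "Stability and retention will be quantitatively assessed with jaw movement" tracking, EMG and force sensors, all with the device in the mouth. The indices are yet to be created.
- Section 3.2.5b: "Tissue adaptation will be assessed by using a 3D laser scanner". The upper arch is scanned, "as will the inner surface of the night guards". The adaptation index is yet to be developed.
- Section 3.2.5c: tissue health by standard dental methods, with no examiner specified.
- Sections 3.2.6 and 3.2.7: daily log, nocturnal EMG, PSG, 3-D scans and microwear. No scorer is named and no rule for scoring bruxism events is given.

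The Equipment part of section 5 says the jaw-tracking analysis will be automated, because "it will allow students to do the data acquisition". The Supplies part says microwear on stone models is screened in the laboratory before the models are sent for confocal analysis.

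**The concern.** Both specific aims hypothesise no significant difference between devices. Under that hypothesis a scoring bias matters in either direction: a shift towards similarity looks like success, and a shift away from it can wrongly count against one device. The plan uses blinding for instructors and subjects but describes none for the people who turn recordings, scans and examinations into data.

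Three places leave room for judgement.

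1. Bruxism events from EMG/PSG have no stated scoring rule, and bruxism episodes per hour is the outcome on which the sample size rests.
2. Tissue health is a live examination.
3. The stability, retention and adaptation indices do not yet exist. Section 4 expects preliminary analyses as soon as data arrive, to check the procedures, so definitions could be settled after someone has seen results by device. The document neither plans nor excludes this.

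Handling the stone models could also disclose the arm, because section 3.2.1 gives them a different use in each group.

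**Working it through.** **Step 1. What is masked, and what could be.** Table 2 lists eight assessment domains.

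| Domain | Material | Room for judgement | Can coding hide the arm? |
|---|---|---|---|
| Subjective fabrication, user satisfaction | Questionnaires | Participant's own | No |
| Stability, retention | Motion, EMG and force files, device in mouth | Index definition; jaw tracking itself automated | Partly |
| Tissue adaptation | 3-D scans, computed volume | Index definition | Partly; the guard itself is scanned |
| Tissue health | Examination | Yes | Yes, if the device is out and the arm is not disclosed |
| Compliance | Daily log, EMG, microwear | EMG reading | EMG yes; log no; microwear uncertain |
| Functional efficacy | EMG/PSG, 3-D scans, microwear | Event scoring | EMG/PSG yes; others in part |

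Five of the eight (stability, retention, adaptation, compliance, functional efficacy) rest wholly or partly on stored material. No masking is described for any of the eight.

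**Step 2. Reproduce the planned sample size.** Inputs from section 3.1: means 3.97 and 4.45 episodes per hour, SD 0.63, alpha 0.05, and 0.8 printed as beta but read here as power. A two-sided test is assumed, since sidedness is not stated.

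- Difference: 4.45 − 3.97 = 0.48. Standardised: 0.48 / 0.63 = 0.762.
- Normal approximation: n = 2 × (1.960 + 0.842)² / 0.762² ≈ 27.0, or 28 per group after rounding up.
- Exact t-test: 28.04, or 29 per group after rounding up. This matches the plan.
- Power at 29 per group by t-test: 81.4%.

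**Step 3. Illustrate a scoring shift.** The documents give no size for such a bias, so the shift b (in SD units) is an assumption. It is taken to move every score in one arm by the same amount and leave the SD unchanged. With 29 per group, the test statistic follows a t distribution with 56 degrees of freedom and non-centrality (apparent standardised difference) / √(2/29), where √(2/29) = 0.2626.

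- Equal devices: apparent difference = b.
- True difference 0.762, shift towards no difference: apparent difference = 0.762 − b.

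| Assumed b | On the bruxism scale (b × 0.63) | False-positive rate, equal devices | Power, planned bruxism difference |
|---|---|---|---|
| 0 | 0 | 5.0% | 81.4% |
| 0.1 SD | 0.063 per hour | 6.6% | 69.7% |
| 0.2 SD | 0.126 per hour | 11.6% | 55.7% |
| 0.5 SD | 0.315 per hour | 46.5% | 16.5% |

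The last row is an extreme: 0.315 / 0.48 = 66% of the planned difference. The power column applies to bruxism episodes only, because the plan gives no target difference or SD for the fabrication indices. Masking does not change the required 29 per group.

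**The case against.** The strongest reply is that the document is silent, and silence is not evidence that assessors are unmasked. A reader might infer from 3.2.5 that investigators know both the device and the hypothesis. The text does not say so. Its sentence also covers only the four fabrication aspects, so it cannot be extended to every outcome. Both points stand, and the finding is limited to masking not being described.

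A reader might also infer that nearly everything could be read blind at no cost. The documents do not support that either. Scans of the guard's inner surface and recordings with the device in place may show the arm. Section 3.2.6 says microwear is specific to the opposing surface, so a cast may carry the same information. The project has no personnel budget and relies on students, so coding takes real if modest effort.

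Several measures leave little room for a reader's opinion: automated jaw tracking, software-derived volumes and fractal analysis of wear. That narrows the concern but does not remove it. Automation does not decide how an index is defined, and it covers neither tissue examination nor EMG/PSG event scoring, for which no rule is given.

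Finally, this is a preliminary study, and the assumed bias drives the figures in the table. That is accepted, and they are offered as sensitivity only.

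**Conclusion.** The concern holds in limited form. The plan describes no masking to device for any assessor, reader or analyst, and does not name the scorers in 3.2.6 and 3.2.7. The exposure is real for bruxism-event scoring, the tissue-health examination and the indices still to be defined. It is smaller for automated tracking and computed volumes.

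Its size is unknown. With 29 per group, two-sided alpha 0.05 and a uniform shift, even an assumed 0.2 SD would roughly double the false-positive rate or take power for the planned bruxism difference well below its target; at 0.1 SD the false-positive rate hardly moves. Nothing in the documents shows that a shift of either size will occur.

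It would go too far to say that any bias could never be undone. Stored files, scans and casts could be re-read later under a code; live examinations could not. This is a cheap improvement worth making before data collection, not a fatal flaw.

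**What to change.** Add to sections 3.2.5 to 3.2.7:

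1. EMG/PSG files and, where feasible, scans and stone or microwear casts receive a random code before scoring (for casts, before the laboratory quality screen). Readers see no arm label. The collaborating biostatistician holds the key until scores are locked.
2. Definitions of the stability, retention and adaptation indices, and the rule for scoring bruxism events, are fixed in writing before any data are viewed by arm, including in the preliminary analyses of section 4.
3. Tissue health is examined with the device out by an examiner to whom the arm is not disclosed, drawing on existing staff where feasible.
4. The scorer is named by role for each outcome in 3.2.6 and 3.2.7.
5. Outcomes that cannot be fully masked are listed: guard inner-surface scans, device-in recordings, possibly microwear, questionnaires and the daily log.

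The cost is modest file and cast coding plus some scheduling. Sample size, visits and equipment do not change. Masking will be only partial, and reports should say so.

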3. METHODS AND STUDY DESIGNS

3.1 Subjects. Sample size estimations (**Table 1**) are based upon a recent review of RCTs for bruxism management, in which acrylic appliances were evaluated (see Appendix 2 in (Huynh et al., 2007)). The mean \pm 1 SD number of bruxism episodes per hour with an occlusal splint (the gold standard) was 3.97 ± 0.58 , and for a palatal splint, the mean \pm 1 SD was 4.45 ± 0.63 . Using these means and the higher SD (0.63), along with an $\alpha = 0.05$ and $\beta = 0.8$, I determined that a study would be sufficiently powered with sample sizes of 29 per group. Based on other Michigan studies, I have estimated recruitment, exclusion and attrition rates, which suggest an estimated initial screening sample size of 120 necessary to end up with 29 per group (**Fig. 1**). There will be two treatment groups: a group receiving supervised training in the fabrication of the SOVA night guard (SOVA) and a group receiving the Michigan custom-acrylic bite splint (MI BS). Two groups times 29 subjects per group equals 58 total needed for analysis (**Fig. 1**, bottom).

Table 1. Treatment (Tx) groups & sample sizes (N).

[figure not shown]
Tx	SOVA	MI BS
N	29	29

Care will be taken to match the randomized groups for age, ethnicity, gender and TMD signs/symptoms. Alternatively these will be modeled as nuisance variables if attrition rates create bias and/or there is a lack of sufficiently sized screening pools. Subject inclusion criteria will be: (1) adults, male or female, (2) clinical signs of dental wear, (3) report from significant others of nocturnal grinding and clenching noises from potential subject, (4) absence of outstanding dental and medical conditions, including cardiovascular disease, sleep apnea, and diagnosed sleep disorders, (5) full dentition sans 3rd molars, (6) no movement or neurological disorders, (7) no active orthodontics, (8) no outstanding or previous periodontal problems, (9) no removable prostheses, (10) no medication use with movement disorders as known side effects, (11) ability to follow instructions, (12) ability to report to the clinical laboratory at appointed times over the course of the study. The presence or absence of TMD joint noises or masticatory myalgia will be permitted; however, joint arthritides will not be permitted.

3.2 Project design.

Fig. 2 provides an overview of the project flow. Each aspect will be described below.

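### Section 3.2.5b bases tissue adaptation on gap volume with no stated normalisation for covered area, so fit is mixed with coverage if the two devices cover different amounts of tooth

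*Combined protocol and SAP*

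**What the plan says.** Section 3.2.5 of the combined protocol and SAP lists tissue adaptation as one of four fabrication aspects and describes it as "how much spacing exists between the maxilla and the device and between the device and mandible". That is a question about fit.

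Section 3.2.5b gives the measurement. "The occlusal, facial and lingual surfaces of the upper arch will be scanned as will the inner surface of the night guards". An index of "adaptation will be developed based on the volumetric spaces separating the teeth from the device, using topological software". The one scoring rule is "Smaller volumes will represent better tissue adaptation", and the comparison is "Volumetric indices will be compared between devices via ANOVA or appropriate statistical methods".

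I found no denominator, common tooth region, or covariate for coverage or arch size in these sections. The matching and nuisance variables in section 3.1 are age, ethnicity, gender and TMD signs or symptoms. Section 3.2.5a, by contrast, says of its own two measures: "Deviations will be used to form standardized indices of stability and retention, with smaller values representing greater stability and retention". The adaptation index is not described as standardised.

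**The concern.** A volume of space has two components: how wide the gap is, and how much surface it extends over. Only the first is fit. A smaller volume may therefore mean a closer fit or simply less tooth covered.

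Randomisation does not separate the two, because coverage belongs to the device. Under section 3.2.3 subjects form the SOVA guard themselves following the manufacturer's instructions, while the acrylic splint is made by standard clinical practice. Nothing in the plan makes coverage the same in both arms, so any difference in coverage is fully confounded with treatment.

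Specific Aim 1 hypothesises no significant difference in fabrication efficacy, so two errors are possible. A difference in coverage could be read as a difference in fit, or it could offset a real difference in fit and leave the hypothesis apparently supported.

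**Working it through.** **The plan's own figure.** The only computed design figure is 29 per group in section 3.1, based on bruxism episodes per hour: means 3.97 and 4.45, SD 0.63, alpha 0.05, and the stated beta of 0.8 read as power of 0.8. The difference is 4.45 − 3.97 = 0.48, or 0.48/0.63 = 0.76 SD. A two-sided t-test needs 28.04, rounded up to 29, so the figure reproduces (power at 29 is 81.4%). It was not derived for tissue adaptation. I use it only as the number analysed per group.

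**Geometry.** Write V for gap volume, A for covered area and g for mean gap:

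V = A × g

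If both devices have the same mean gap and one covers a fraction k of the area the other covers, the ratio of mean volumes is k. With k = 0.8 the volume is 20% smaller at identical fit.

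**Size of the effect on a test.** The documents give no gap, area or coverage figure, so the inputs here are assumptions: between-subject CV of volume 15%, 25% or 40%, the same SD in both arms, and equal mean gap. The spurious standardised difference is (1 − k)/CV. The probability of rejection comes from the two-sided two-sample t-test at 0.05 with 29 per group.

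| Less coverage | CV 15% | CV 25% | CV 40% |
|---|---|---|---|
| none | 0 SD, 5% | 0 SD, 5% | 0 SD, 5% |
| 10% | 0.67 SD, 70% | 0.40 SD, 32% | 0.25 SD, 15.5% |
| 20% | 1.33 SD, 99.9% | 0.80 SD, 85% | 0.50 SD, 46.5% |
| 30% | 2.00 SD, about 100% | 1.20 SD, 99% | 0.75 SD, 80% |

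**Check by simulation.** Gap and area were drawn separately (gap CV 15% to 40%, area CV 8% to 10%, log-normal, 20,000 trials of 29 per group). Volume gave false differences in 16% to 64% of trials at k = 0.9 and in 53% to 99.8% at k = 0.8. Volume divided by area stayed at about 5% throughout. At k = 1 both measures stayed at about 5%.

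**Masking.** If one device has a 25% wider gap and 20% less coverage, the volume ratio is 1.25 × 0.8 = 1.00. In the same simulation volume rejects in about 5% of trials, while volume divided by area rejects in 55% to 99.98%.

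**Arch size.** This is a subject characteristic, so randomisation balances it in expectation. Its effect is on variance: CV²(V) = (1 + CV²(g))(1 + CV²(A)) − 1. With gap CV 40% and area CV 10%, this is 1.16 × 1.01 − 1 = 0.1716, against 0.16 for the gap alone, or 7% more. With gap CV 15% and area CV 8%, it is 1.0225 × 1.0064 − 1 = 0.0290, against 0.0225, or 29% more.

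**The case against.** The strongest reply is that the index has not been defined yet. The text says it will be developed from volumes, and the sentence on smaller volumes gives a direction of scoring, not a formula. A reader might infer that the trial will compare raw, unadjusted volumes, but the documents do not say so and do not exclude a denominator. This stands. What remains is that the plan commits to a direction on volume and names no normalisation. The open wording on statistical methods does not supply one either: a test recovers fit from volume only if area is brought in, and area is not mentioned.

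Second, coverage may not differ. A reader might infer that one of the two devices is favoured. Neither device's covered area is given, so the documents support neither the existence of a bias nor its direction. At equal coverage there is none.

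Third, total space is one literal reading of how much spacing exists, and mean gap alone ignores how much tooth is covered. That is fair, and it is the reason to report covered area as well.

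Finally, this is one of several fabrication measures in a study that calls itself preliminary, and it did not drive the sample size. That limits the severity.

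**Conclusion.** The point holds in conditional form. As written, the scoring rule confuses fit with extent whenever the devices differ in coverage, and it can mislead in either direction. Across the assumed CVs of 15% to 40%, the chance of a false significant difference runs from the nominal 5% at equal coverage to between 46.5% and 99.9% at 20% less coverage. Those figures rest on assumed CVs, an assumed coverage difference and equal mean gap. They show how sensitive the measure is and do not predict what this trial will find.

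A reader might also infer that differing arch sizes bias the comparison. Randomisation rules that out in expectation. Under the assumed CVs, arch size raises the variance by about 7% to 29% and does nothing systematic.

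This is a cheap improvement, nice to have.

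**What to change.** Before any adaptation data are seen, define the index as gap volume divided by the tooth-surface area the device covers, both taken from the scans already planned. The result is a mean gap in millimetres. Compare that between devices, and report covered area separately by device so that a difference in extent is visible in its own right.

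Optionally, add a sensitivity analysis over an anatomical tooth region defined in advance and applied to every scan. It would guard against the devices covering parts of the tooth where gaps naturally differ. The region has to be anatomical because each subject receives only one device, so no subject has a surface that both devices cover.

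The main index costs one division, with no new visit, equipment or subjects. The common-region analysis would need some extra scan processing.
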